## 1.2. Study Design

Overview of Study Design and Key Features	
Study Schematic for Cohort 1: Full Intensive PK Sampling as Inpatient <pre> graph LR     SV[Screening Visit (Day -1 to Day 1 Pre-Dose)] --> CC[Clinic Confinement]     CC --> OP[Outpatient]     SV --> F1[Female adults participants with suspected uUTI based on clinical presentation and pyuria and nitrite]     F1 --> CC     CC --> PDC[Pre-Dose Check-in to clinic (Day -1 or 1)]     PDC --> OT[On-Therapy (Day 1 to 5)]     OT --> COT[Check out from clinic & On-Therapy period (Day 6)]     COT --> TOC[ToC Visit (Day 10 to 13) 5 to 8 days post treatment]     TOC --> FUV[Follow-up Visit (28±3 days after the start of treatment)]     OT --> PTPA[Post treatment PK analysis (urine and blood)]     PTPA --> FUV     CC --> B[Baseline: • Clinical symptoms assessment & scores • Urine Bacteriology CCI]     OP --> PT[Post treatment: • Clinical symptoms assessment & scores • Urine bacteriology CCI] </pre>	
Study Schematic for Cohort 2: Reduced PK Sampling as Outpatient <pre> graph LR     SV[Screening Visit (Day -1 to Day 1 Pre-Dose)] --> OCC[Optional Clinic Confinement]     OCC --> OP[Outpatient]     SV --> F2[Female adult participants with suspected uUTI based on clinical presentation and pyuria and nitrite]     F2 --> OCC     OCC --> PDC[Pre-Dose Check-in to clinic (Day -1 or 1)]     PDC --> OT[On-Therapy (Day 1 to 5)]     OT --> COT[Check out from On- Therapy period (Day 6)]     COT --> TOC[ToC Visit (Day 10 to 13) 5 to 8 days post treatment]     TOC --> FUV[Follow-up Visit (28±3 days after the start of treatment)]     OT --> PTPA[Post treatment PK analysis (urine and blood)]     PTPA --> FUV     OCC --> B[Baseline: • Clinical symptoms assessment & scores • Urine bacteriology CCI]     OP --> PT[Post treatment: • Clinical symptoms assessment & scores • Urine bacteriology CCI] </pre>	
Design Features	
This Phase 1b study is a double-blind, double-dummy, nitrofurantoin-controlled study designed primarily to evaluate microbiological response at the ToC visit and safety, tolerability and PK response following CCI oral dosing for 5 days of GSK3882347 in adult female participants with uUTI. Nitrofurantoin will be included in the study to ensure unbiased reporting of safety events. The clinical response CCI with GSK3882347 will be evaluated as exploratory endpoints in this study.
 
CCI
 
The study will be separated into 2 cohorts. Cohort 1 will have an inpatient Treatment period and PK analysis will be conducted at frequent timepoints. Cohort 2 will have an outpatient Treatment period and PK analysis will be conducted less frequently, at key trough timepoints. The treatment period will consist of 5 days and the total study duration will be up to 31 days.

Study intervention	
 
1. GSK3882347 CCI mg oral capsules CCI for 5 days.
 
2. Nitrofurantoin 100 mg oral capsule BID for 5 days.
 

Overview of Study Design and Key Features	
Study intervention Assignment	All participants who provide informed consent and meet the study entry criteria will be randomized to receive either CCI mg GSK3882347 or 100 mg BID nitrofurantoin in a 3:1 ratio.
CCI	

## 2. STATISTICAL HYPOTHESES

No formal statistical hypotheses will be tested in this study.

### 2.1. Multiplicity Adjustment

N/A

### 3. ANALYSIS SETS

Analysis Set	Definition / Criteria	Analyses Evaluated
Screened	All participants who signed the ICF and were screened for eligibility.	
 
Study Population
 

Enrolled	
All participants who passed screening and entered the study
 
Note: screening failures [who never passed screening even if rescreened] and participants screened but never enrolled into the study [Met eligibility but not needed] are excluded from the Enrolled analysis set as they did not enter the study.)
	
 
Study Population
 

Randomized	
All participants in the Enrolled analysis set who were randomly assigned to study intervention in the study.
 
Participants will be analyzed according to the intervention they were randomly assigned to.
	
 
Study Population
 

Safety	
All participants in the Randomized analysis set who receive at least 1 dose of study intervention.
 
Participants will be analyzed according to their actual intervention received.
	
 
Safety
 

Microbiological Modified Per Protocol (Micro-MPP)*	
All participants in the Safety analysis set who: receive all planned doses of study intervention; have a Qualifying baseline E. coli from a quantitative bacteriological culture of a pre-treatment clean-catch midstream urine specimen; have completed a ToC visit; have no major protocol deviations that would prevent evaluation of microbiological response.
 
Participants will be analyzed according to their actual intervention received.
	
 
Efficacy
 

CCI

CCI

Analysis Set	Definition / Criteria	Analyses Evaluated
CCI		
Pharmacokinetic (PK)	
All participants in the Safety analysis set who had at least 1 non-missing PK assessment (Non-quantifiable [NQ] values will be considered as non-missing values).
 
Participants will be analyzed according to their actual intervention received.
	
 
Pharmacokinetic
 

CCI		

\*The algorithm for determining qualifying *E. coli* based on microbiology laboratory quantitative culture results is provided in the [Appendix 4](#)

CCI

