### 6.8.3. Rescue Medicine

If participants do not respond clinically (participants experience new, worsening or non-resolving signs and symptoms of uUTI) to randomised medication, they should be given rescue medication. They will be considered a treatment failure and will be provided rescue medication by site as per SoC [Gupta, 2011].

Use of rescue medications is allowable at any time during the study. The requirement for the use of rescue medications should be assessed by the Investigator in accordance with site procedure and treatment guidelines [Gupta, 2011]. If clinically acceptable (and onset of a severe infection is not suspected), rescue medication should be postponed until the next clinical symptom resolution assessment during the On-Therapy period.

Pathogen identification or in vitro resistance of recovered uropathogens alone, is not a reason for study treatment discontinuation through the On-Therapy period. Patients can resolve their infection spontaneously and in the absence of treatment [Little, 2009].

The date and time of rescue medication administration as well as the name and dosage regimen of the rescue medication must be recorded.

Rescue medication to be prescribed by Site Investigator as required and as assessed by the Investigator and in consultation with the Medical Monitor if required by the Investigator. The decision to prescribe rescue medication resides with the Investigator. A combined clinical and laboratory (e.g. serum creatinine and other haematological and biochemical parameters) assessment should be used to prior to withdrawal of study intervention.

The Investigator can request the participant's baseline, enrolling microbiology culture to help in the assessment and additional suitable SoC if required [Gupta, 2011]. Note: The potential for a drug-drug interaction with next line therapy (e.g., trimethoprim-sulfamethoxazole) has been reviewed and is permitted in the study.

If antibiotic rescue medication is given, the participant will complete an early discontinuation visit as per the SoA and will not be required to attend any other subsequent visits.

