### **9.2. Analysis Sets**

For purposes of analysis, the following populations are defined.

Population	Description
Randomized Population	All participants randomly assigned to study intervention.
Safety Population	All randomized participants who receive at least 1 dose of study intervention. Participants will be analyzed according to their actual intervention received.
PK Population (Sub populations identified for Cohort 1 and Cohort 2)	All randomized participants who have a valid PK sample taken and from whom a measurable plasma or urine concentration, even if the concentration below assay's limit of quantification, (for the actual study intervention) received.  Separate Sub populations will be constructed for participants Randomised to Cohort 1 and Cohort 2 who were in the PK population. [Note: these sub-populations support analyses

Population	Description
	involving PK parameters that can only be derived from a full intensive PK time profile].
Microbiological Modified Per Protocol (Micro-MPP) Population*	All participants randomly assigned to study intervention who receive all planned doses of study intervention and have a Qualifying baseline E. coli from a quantitative bacteriological culture of a pre-treatment clean-catch midstream urine specimen.

\*The algorithm for determining qualifying *E. coli* based on microbiology laboratory quantitative culture results is provided in the Section 10.8.

Details of additional populations, including targeting non-*E. coli* will be provided in the SAP.

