### 1.1.1. Estimand for Primary Endpoint

The primary clinical question of interest is: *What is the microbiological response for GSK3882347 assessed at ToC in participants with acute uUTI caused by E. coli at Baseline who completed the planned course of treatment (5 days) and had no major deviations from protocol that would prevent evaluation of microbiological response (as defined in the protocol deviation rules document). Use of rescue medication after last dose of study intervention will be set to non-responder in the endpoint definition.*

The Primary estimand is described by the following attributes:

- Population: Female participants with acute uUTI with a qualifying baseline *E. coli* (Section 6.4) at baseline who completed the planned course of treatment (5 days) and had no major deviations from protocol that would prevent evaluation of microbiological response
- Treatment condition: GSK3882347 CCI mg given orally CCI for 5 days or Nitrofurantoin 100mg given orally twice daily for 5 days.
- Variable: Microbiological response at ToC visit (see Section 4.2.1)
- Summary measure: Frequency and percentage of participants with microbiological response (responder/non-responder) in GSK3882347 treatment group
- Main intercurrent events anticipated:

- Use of rescue medication prior to ToC visit- Composite strategy
- This intercurrent event is captured through the definitions of microbiological response (see Section 4.2.1). Hence the participants who take rescue medication prior to ToC visit will be considered as non-responders.
- Participants who are lost to follow-up prior to ToC, have a missing/ unevaluable sample at ToC, discontinue study treatment due to any reason (withdrawal of consent/AEs/missed doses) will not be included in the analysis and may be replaced at the discretion of the Sponsor.
- Rationale for estimand:

Use of rescue medication may impact microbiological outcomes and its use implies that the treatment the participant received is not working, therefore, the definition of a successful microbiological response precludes the use of rescue medications. In this small, early phase, proof of mechanism study, interest lies in the treatment effect of participants who completed the planned course of treatment and follow important components of the study protocol to establish proof of mechanism.

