#### 4.4. Exploratory Endpoint(s) Analyses

Efficacy results will be presented on the Micro-MPP analysis set, unless otherwise specified.

CCI

- Clinical resolution response
- Clinical symptom score outcome & response

CCI

A blinded clinical review of concomitant medications will be conducted to determine use of systemic antibacterials.

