		respectively CCI from a quantitative bacteriological culture of a pre-treatment clean-catch midstream urine specimen.	
Amendment 3	CCI		
	
 
For primary endpoint estimand: Use of rescue medication will be set to non-responder in the endpoint definition.
 
	
 
Use of rescue medication after last dose of study intervention will be set to non-responder in the endpoint definition.
 
	
 
Wording for primary estimand updated to clarify that rescue medication use for population of interest would only occur following the 5 day dosing period.
 

	
 
For secondary endpoints estimand: Use of rescue medication – While on treatment strategy
 
	
 
Use of rescue medication – Treatment policy strategy
 
	
 
Strategy for handling of ICE for estimand for Secondary endpoint – Safety so that all safety data is presented in summaries.
 

	
 
For secondary endpoints estimand: estimand specified for plasma and urine PK parameters
 
	
 
For secondary endpoints estimand: estimand specified for plasma and urine PK concentrations
 
	
 
Updated to align with protocol defined secondary endpoints
 

CCI

CCI

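### The completed-ToC criterion in SAP 3 removes participants rescued between last dose and ToC whom the primary estimand counts as failures

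*SAP*

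**What the plan says.** **The rule for rescue.** SAP 1.1.1 handles rescue before ToC by a composite strategy: "Hence the participants who take rescue medication prior to ToC visit will be considered as non-responders". Protocol 9.3.2 likewise counts it as failure. The primary question in SAP 1.1.1 limits the rule to rescue after the last dose. SAP Table 2 explains that "rescue medication use for population of interest would only occur following the 5 day dosing period".

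**The analysis set.** SAP 3 defines Micro-MPP as participants who "receive all planned doses of study intervention; have a Qualifying baseline" *E. coli*, and who "have completed a ToC visit; have no major protocol deviations that would prevent evaluation of microbiological response". Protocol 9.2 defines the set under the same name as "All participants randomly assigned to study intervention who receive all planned doses of study intervention and have a Qualifying baseline" *E. coli*; it has no ToC-completion criterion.

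**The visit schedule after rescue.** Protocol 6.8.3 states that if antibiotic rescue is given, "the participant will complete an early discontinuation visit as per the SoA and will not be required to attend any other subsequent visits". Protocol 7.1 says the same where the need for rescue ends study treatment.

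**Missing ToC data.** SAP 1.1.1 and Protocol 9.3.2 leave participants with no evaluable ToC sample out of the analysis and let the sponsor replace them.

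**Use of the set.** SAP 4.2 runs the primary analysis on Micro-MPP. SAP 4.4 adds: "Efficacy results will be presented on the Micro-MPP analysis set, unless otherwise specified".

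**The concern.** The composite strategy is meant to keep rescued participants in the denominator as failures. Once the estimand is restricted to treatment completers, the only people it can act on are those rescued between last dose and ToC. These are also the people whom the protocol releases from the ToC visit, and SAP 3 makes that visit a condition of entry. One part of the plan scores them as failures, and another removes them.

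The error has one direction. Dropping a failure can only raise the rate above the composite rate that the estimand describes. Replacement makes the loss harder to see, because randomization stops when about 21 evaluable participants on GSK3882347 have completed ToC (Protocol 1.1). Protocol 9.3.1 names microbiological response as the key endpoint for internal decisions. No hypothesis is tested, so the percentage and its exact interval are what the reader will act on.

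The same gap affects clinical resolution at ToC. SAP 4.4.3 treats failure to attend a visit as a clinical failure, but a set limited to ToC completers contains nobody who missed ToC.

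**Working it through.** **Step 1: follow a participant through the rules.** Dosing covers Days 1 to 5 and ToC falls on Days 10 to 13 (schedules of activities). Assume a qualifying baseline *E. coli* and no other reason for exclusion.

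| Rescue starts | All doses? | ToC completed? | In Micro-MPP? | Status under the estimand |
|---|---|---|---|---|
| Days 1–5, stopping study drug | No | not relevant | No | Outside the declared completer population |
| After last dose, before ToC; required visits only | Yes | No | **No** | **Non-responder** |
| After last dose, before ToC; attends ToC anyway | Yes | Yes | Yes | Non-responder; the rule works |
| After ToC | Yes | Yes | Yes | ToC culture decides |

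Only the second row conflicts. SAP 1.1.1 states both the composite rule and the missing-ToC exclusion, and no visible text says which takes precedence when both apply. The set definition in SAP 3 settles it in favour of exclusion.

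**Step 2: figures available.** The usable number is the target of about 21 evaluable ToC completers on GSK3882347. The plan's maxima of 122 and 141 randomized at 3:1 imply evaluability of 21/(0.75 × 122) = 23.0% and 21/(0.75 × 141) = 19.9%. The planned evaluability rates are not visible, so this is no independent check. No rescue rate and no expected response rate are visible either.

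**Step 3: effect on an observed rate.** Let x be successes among the 21 retained and k the number dropped from the second row. The reported rate is x/21; the composite rate is x/(21 + k). Both x and k are assumptions. Intervals are 95% Clopper-Pearson, the SAP's method.

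| x | k | Reported | Composite | Gap (points) |
|---|---|---|---|---|
| 14 | 1 | 66.7% (43.0–85.4) | 14/22 = 63.6% (40.7–82.8) | 3.0 |
| 14 | 3 | 66.7% (43.0–85.4) | 14/24 = 58.3% (36.6–77.9) | 8.3 |
| 14 | 5 | 66.7% (43.0–85.4) | 14/26 = 53.8% (33.4–73.4) | 12.8 |
| 8 | 3 | 38.1% (18.1–61.6) | 8/24 = 33.3% (15.6–55.3) | 4.8 |
| 8 | 5 | 38.1% (18.1–61.6) | 8/26 = 30.8% (14.3–51.8) | 7.3 |

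**Step 4: expected gap.** Let p be the success rate among those retained and r the share of otherwise eligible participants who fall in the second row. The reported rate estimates p, the composite rate is p(1 − r), and the gap is p × r. For p from 0.4 to 0.7 this is 2.0 to 3.5 points at r = 5%, 4 to 7 at r = 10%, and 8 to 14 at r = 20%. At r = 0 it is zero.

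**The case against.** A reader might infer that no rescued participant can ever be scored a failure. The documents do not support that. Later visits are not required, but they are not barred, and a participant who attends ToC stays in the set as a failure. The visit rule in Protocol 6.8.3 is worded for antibiotic rescue. The early discontinuation visit collects a urine microbiology sample, and no visible text says how such a visit on Days 10 to 13 is classified.

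A reader might also object to losing participants rescued on Days 1 to 5. That is not an inconsistency. Protocol 3 and SAP 1.1.1 restrict the question to those who completed the planned course and give a proof-of-mechanism reason. Counting on-treatment rescue as failure would answer a different question.

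Nor do all rescued participants vanish from the clinical endpoints. SAP 4.4 allows exceptions, rescue after ToC removes nobody from the set, and SAP Table 1 assigns some systemic antibacterial use before Follow-up to failure.

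Redaction also limits what can be said. Further analysis sets, the ToC outcome tables in SAP Appendix 6 and part of SAP 4.2.2 are hidden. SAP Table 2 mentions a Micro-MITT set needing only one dose, whose use is not visible. A supportive analysis may therefore retain rescued participants. It would not change who enters the primary set.

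Finally, this is a descriptive Phase 1b estimate with no test. That limits the consequences, but with about 21 participants a few exclusions still move the headline rate.

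**Conclusion.** The point holds for one group: participants who took all planned doses, received antibiotic rescue after the last dose and before ToC, and followed only the required schedule. The estimand calls them non-responders and SAP 3 excludes them. As written, the composite strategy may act on few or no participants.

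The primary response rate would be biased upward if any such participant is dropped. It would be wrong to say that it is inflated as a matter of fact, because the number dropped is unknown and could be zero. At an observed 14/21, one dropped participant is worth about 3 points and three are worth 8.3. These figures rest on assumed counts. They should not be read as covering on-treatment rescue, which the completer estimand excludes openly.

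**What to change.** 1. In SAP 3, let the visit criterion be met either by a completed ToC visit or by systemic antibacterial rescue after the last dose and before ToC. Protocol 9.2 has no ToC criterion, so nothing needs replacing there.
2. Score these participants as microbiological failures, and as clinical resolution failures at ToC, whether or not they attend.
3. State in SAP 1.1.1 and Protocol 9.3.2 that the missing-ToC exclusion and replacement do not apply to them. Say also how they count toward the 21 at which randomization stops, since that is a count of ToC completers.
4. Report rescue-related exclusions from Micro-MPP by arm.
5. Keep the all-planned-doses condition. A rate that also counts on-treatment rescue as failure can be added as a labelled supplementary analysis.

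The cost is SAP wording, a matching clarification in the protocol text, and one derivation. Protocol 6.8.3 already requires the date and time of rescue to be recorded. No visit, dose or clinical rule changes. The reported rate may be slightly lower.

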## 4. STATISTICAL ANALYSES

### 4.1. General Considerations

#### 4.1.1. General Methodology

Summary tables will provide the following descriptive statistics as a minimum, unless otherwise specified:

- Continuous data (natural scale):  
n, mean, standard deviation (SD), median, minimum and maximum.
- Continuous data (log-transformed):  
n, geometric mean, %CV, median, minimum and maximum.

- Categorical data:  
number and percentage of participants in each category.

All analyses (excluding PK) will be presented on combined cohorts (Cohort1 + Cohort 2), unless otherwise specified.

Details of the planned displays are provided in OPS and will be based on GSK Data Standards and Statistical Principles.

#### 4.1.2. Baseline Definition

For all endpoints the baseline value will be the latest pre-dose assessment with a non-missing value, including those from unscheduled visits. If time is not collected, Day 1 assessments are assumed to be taken prior to first dose and used as baseline.

The mean will be considered for triplicate measurements taken at the latest pre-dose assessment. If the latest pre-dose assessment is missing, then the previous assessment time point would be considered as baseline where possible (i.e. if Day 1 (Pre-dose) is missing the Day -1 will be used) unless specified otherwise.

Parameter	Study Assessments Considered as Baseline		Baseline Used in Data Display
	Screening/ Day -1	Day 1 (pre- dose)	
Efficacy			
Microbiological response		x	Day 1(pre-dose)
UTI Clinical Symptom Score Assessment	x	x	Day 1(pre-dose)
CCI			
Quantitative Bacteriology Culture		x	Day 1(pre-dose)
CCI			
Safety			
12-lead ECG	x		Day -1
Vital sign	x	x	Day 1(pre-dose)
Haematology*	x	x	Day 1(pre-dose)
Clinical chemistry*	x	x	Day 1(pre-dose)
Urinalysis*	x	x	Day 1(pre-dose)
PK			
PK urine sample (Cohort 1)		x	Day 1(pre-dose)

Parameter	Study Assessments Considered as Baseline		Baseline Used in Data Display
	Screening/ Day -1	Day 1 (pre-dose)	
PK plasma sample (Cohort 1)		x	Day 1(pre-dose)

\* If baseline data is missing, then change from baseline calculations will not be performed and will be set to missing.

## 4.2. Primary Endpoint(s) Analyses

The primary endpoint to be estimated is microbiological response at ToC visit in female participants with a qualifying baseline *E. coli*. The Micro-MPP analysis set will be used for the analysis and the results will be summarised by treatment group.

#### 4.2.1. Definition of endpoint/estimand

The microbiological response to the study treatment will be determined by a prespecified programmed algorithm for each participant, considering the number of baseline qualifying uropathogens based on their microbiology laboratory quantitative culture results. The algorithm for determining qualifying *E. coli* is provided in the [Appendix 4](#) and the detailed definitions for response are provided in Appendix 6.

Details on estimands are provided in the Section 1.1.1.

